### **PTAE leading to withdrawal**

A PTAE leading to withdrawal is a PTAE listed as the reason for the subject not being randomized to treatment on the “Study Termination” CRF.

### **AE leading to death**

An AE leading to death is an AE with outcome equal to “Fatal” on AE CRF.

### **Amlodipine dose and celecoxib dose**

The following variables will be derived for the logistic models:

Treatment group	Amlodipine dose	Celecoxib dose
Amlodipine + Celecoxib	10 mg	200 mg
Amlodipine + Placebo	10 mg	0 mg
Placebo + Placebo	0 mg	0 mg

### **Count of AEs**

Two AEs with the same PT and classified in the same category (PTAE or TEAE) that do not overlap in date of occurrence will be considered as two different events when calculating the “number of events” in the tables.

Secondary safety variables will include physical examination, body weight, vital signs, orthostatic hypotension evaluations, ECG, hematology, serum chemistry, and urinalysis.

### **Physical examination**

The protocol-specified organ or body systems for the comprehensive physical examination will be used in the summary tabulation [i.e., skin; head, eyes, nose and throat; thyroid; lungs; cardiovascular; abdomen (liver, spleen), lymph nodes, extremities, and neurological (abbreviated exam)]. The targeted physical examination findings will only be provided as a listing.

### **Body weight**

Body weight will serve a dual function as both a secondary efficacy endpoint (see Section 6.2) and as a safety endpoint. For the latter, the body weight and change in body weight for the Safety population will be used for analysis.

### **Vital signs**

Clinic visit resting systolic and diastolic blood pressure, pulse rate, respiration rate, and oral body temperature will be used for analysis.

For resting systolic and diastolic blood pressures, the Average values of 3 recordings reported in the CRF (derived) will be used in the analysis. The recordings 1, 2 and 3 will be only listed.

The continuous recording of BP by ABPM will serve a dual function as both the official BP values for all efficacy determinations and calculations and as additional BP assessments for safety. For the latter, the analyses will use the Safety population.

### **Orthostatic hypotension evaluation**

The average values of 3 recordings in supine position reported in the CRF (derived) will be used in the analysis. The recordings 1, 2 and 3 (Start after 5 minutes rest in supine position) will be only listed.

The orthostatic hypotension at each visit will be recalculated. It will be considered equal to “Yes” if at least one of the following conditions will occur:

- the average SBP after supine for 5 minutes minus the SBP 1 minute after standing is greater than 25 mmHg;
- the average SBP after supine for 5 minutes minus the SBP 3 minutes after standing is greater than 25 mmHg;
- the average DBP after supine for 5 minutes minus the DBP 1 minute after standing is greater than 15 mmHg;
- the average DBP after supine for 5 minutes minus the DBP 3 minutes after standing is greater than 15 mmHg.

Otherwise it will be considered equal to “No”.

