8.4 Orthostatic Hypotension Evaluations

Orthostatic hypotension will be evaluated at baseline (Day 0), Day 7, and Day 14.

For this determination, the subject will be placed supine for 5 minutes. At the end of that time a manual BP will be assayed three times. The average of these three will be used as the baseline value. The subject will then be asked to stand vertically and two manual BPs will be obtained: the first will be one minute after standing and the second will be three minutes after standing. Orthostatic hypotension will be defined as a decrease in systolic BP of > 25 mmHg from baseline in either of the readings, or a decrease in diastolic BP of > 15 mmHg in either of the readings compared to the baseline average.

In addition to these quantitative measurements, specific comparisons in reported AE rates for terms associated with hypotension will be made. These events will include dizziness, falls, light-headedness, and vertigo.

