## 7. Statistical Methodology

### 7.1. Handling of Missing Data

For ITT and mITT population, if at the time of the Day 7 clinic visit subjects have a too elevated BP to be able to continue safely in the study (i.e., SBP24h > 169 mmHg or DBP24h > 110 mmHg), blood will be drawn for renal profile testing, the study drug will be discontinued and the subjects will be instructed to resume taking their prescribed BP medication as directed by the study doctor or general practitioner. In case of missing data, LOCF techniques will be used as follows:

1. ITT population: LOCF from baseline (Day 0)
2. mITT population: LOCF from Day 6

Using this method, the end of study measurement is either Baseline, Day 6 or Day 13.

No specific analysis for withdrawn patients will be presented.

The number of patients with missing data will be presented under the “Missing” category, if present. Missing values will be included in the denominator count when computing percentages.

When continuous data are being summarized, only the non-missing values will be evaluated for computing summary statistics.

Missing or incomplete data will be treated as described in sections 5, 6.4, 6.5, 7.1, 7.9, 7.10. Other critical missing data will be discussed prior to treatment unblinding, if any. Decisions will be taken during the data review and will be fully documented in the Data Review Report.

The LOCF method of imputation will be applied for missing values in all ANCOVA models. This method will not be applied to the descriptive statistics.

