### **Orthostatic hypotension evaluation**

The orthostatic hypotension evaluation BP values will be summarized for the Safety population by treatment group at each applicable visit (Day 0, Day 7, and Day 14) by descriptive statistics (n, mean, SD, median, and range). In addition, at each visit after baseline, change from baseline will be calculated and summarized by descriptive statistics (n, mean, SD, median, and range). Baseline will be Day 0. The above analysis will be performed for each of the following:

1. Average BP after 5 minutes rest in supine position (average of 3 recordings)
  - a. SBP
  - b. DBP
2. BP 1 minute after standing
  - a. SBP
  - b. DBP
3. BP 3 minutes after standing
  - a. SBP
  - b. DBP
4. Difference between average BP after 5 minutes rest supine and BP 1 minute after standing
  - a. SBP
  - b. DBP
5. Difference between average BP after 5 minutes rest supine and BP 3 minutes after standing
  - a. SBP
  - b. DBP

Comparisons of the orthostatic hypotension BP measurements among treatment arms using ANCOVA will be presented for each of the above 5 parameters. The change from baseline to Day 14 will be considered.

The number and the percentage of patients with evidence of Orthostatic Hypotension (Yes, No, Missing) will be presented at each visit (Day 0, Day 7, and Day 14) by treatment group. The Chi-Squared/Fisher's Exact test will be provided to test differences between arms.

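### The SAP 6.4 rule for orthostatic hypotension has no branch for missing readings, so an incomplete standing test with no qualifying drop is scored 'No', which is not reconciled with the 'Missing' category in SAP 7.1 and 7.9.

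*SAP*

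**What the plan says.** Protocol 8.4 takes a supine average as the reference, followed by standing readings at one and three minutes. On the systolic side, "Orthostatic hypotension will be defined as a decrease in systolic BP of > 25 mmHg from baseline in either of the readings"; a diastolic fall of more than 15 mmHg in either reading also qualifies. The section does not say what to do when a standing test is not completed.

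SAP 6.4 recalculates the diagnosis at each visit from four differences (systolic and diastolic, at one and three minutes): "It will be considered equal to “Yes” if at least one of the following conditions will occur". Every other case goes to the closing clause, "Otherwise it will be considered equal to “No". Missing readings are not mentioned.

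SAP 7.9 presents the same variable at Days 0, 7 and 14 with three levels: "The number and the percentage of patients with evidence of Orthostatic Hypotension (Yes, No, Missing) will be presented at each visit". For the comparison of arms, a chi-square or Fisher's "Exact test will be provided to test differences between arms"; the section does not say whether 'Missing' subjects enter it.

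SAP 7.1 gives the general rules: "The number of patients with missing data will be presented under the “Missing” category, if present" and "Missing values will be included in the denominator count when computing percentages". It also refers incomplete data back to several sections, 6.4 among them.

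**The concern.** A negative result under the protocol definition needs both standing readings, because a fall in either one is enough for a positive. SAP 6.4 gives 'No' on less than that. A subject with one standing reading below the limits and the other absent, or with neither reading, is counted as a confirmed negative.

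The 'Missing' level in 7.9 shows that the authors expected undetermined results, but the derivation gives no route to one. Two programmers could follow different sections and produce different tables, each with support in the text.

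Incomplete tests are foreseeable. Protocol 4.3 asks for Day 14 evaluations after withdrawal only where feasible, while the safety population in SAP 4.1 includes everyone dosed. SAP 1.3.9(i) removes the logistic analysis of this diagnosis, so the chi-square/Fisher comparison is its only between-arm test.

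**Working it through.** The plan states no figure on this point, so there is nothing to reproduce. The check applies the 6.4 rule to every pattern of standing readings. Each time point either exceeds a limit, does not exceed, or is missing. For simplicity a reading is taken to supply both systolic and diastolic values or neither, and the supine average is taken as present. This gives 3 × 3 = 9 patterns.

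| 1 minute | 3 minutes | SAP 6.4 as written | With a 'Missing' branch |
|---|---|---|---|
| exceeds | exceeds | Yes | Yes |
| exceeds | does not | Yes | Yes |
| exceeds | missing | Yes | Yes |
| does not | exceeds | Yes | Yes |
| does not | does not | No | No |
| does not | missing | No | Missing |
| missing | exceeds | Yes | Yes |
| missing | does not | No | Missing |
| missing | missing | No | Missing |

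Five patterns contain a missing reading. Two are 'Yes' under either rule and three change from 'No' to 'Missing'. A direct SAS implementation would also give 'No' for those three, because a missing difference does not satisfy a 'greater than' comparison.

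Set against the other sections:

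- Both readings missing: 6.4 gives 'No', while 7.1 and 7.9 call for 'Missing'. This is a contradiction.
- One missing, the other not exceeding: 6.4 gives 'No', and no section clearly reassigns it. SAP 7.1 points back to 6.4.

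The size can only be illustrated. The planned active arm is 105 × 3/7 = 45. Assume 2 'Yes' results in each active arm and k incomplete tests without a qualifying drop, all in arm 1. Both 2 and k are assumptions; the documents give neither an event rate nor a rate of incomplete tests.

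| k | Coded 'No', or 'Missing' kept in denominator | Excluded: 2/(45 − k) | All counted as events: (2 + k)/45 | Fisher p, all counted as events, against 2/45 |
|---|---|---|---|---|
| 1 | 2/45 = 4.4% | 2/44 = 4.5% | 3/45 = 6.7% | 1.00 |
| 2 | 4.4% | 2/43 = 4.7% | 4/45 = 8.9% | 0.677 |
| 3 | 4.4% | 2/42 = 4.8% | 5/45 = 11.1% | 0.434 |
| 5 | 4.4% | 2/40 = 5.0% | 7/45 = 15.6% | 0.157 |

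The first results column does not change, because the 7.1 denominator rule gives the same 'Yes' percentage under either label. Excluding the subjects moves the rate by 0.6 of a point at most here. The large shift appears only if every incomplete test is taken to be a true case.

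**The case against.** The strongest reply is that 6.4 should not be read alone. SAP 7.1 and 7.9 show that a wholly absent test was meant to appear as 'Missing', and 7.1 sends other critical missing data to a documented review before unblinding. That is fair as to intent, and it means a reader should not conclude that the 'Missing' row will necessarily be empty. It does not settle the partly missing test, and it leaves 6.4 contradicting the table it feeds.

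A reader might infer that any missing standing reading produces 'No'. It does not: if the other reading exceeds its limit, the result is 'Yes'.

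A reader might also infer that the rule hides harm, because subjects who become dizzy sit down before the readings are taken. That is plausible, but neither document gives reasons for, or a frequency of, incomplete standing tests, so a direction of bias cannot be claimed.

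It is also tempting to say that each affected subject moves an arm's rate by about 2 points (1/45 = 2.2%). That holds only if the subject is a true case.

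Finally, other analyses give partial cover. SAP 6.4 and 7.9 compare adverse events coded as orthostatic hypotension, dizziness, postural dizziness, fall or vertigo. SAP 7.9 also summarises the standing pressures with their n and analyses the changes by ANCOVA. This limits the consequence but does not correct the derived diagnosis.

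**Conclusion.** The point holds as a conflict between a stated derivation and the table and missing-data rule that go with it. Under 6.4 as written, three of the five patterns with a missing standing reading are scored as negatives. One of these contradicts 7.1 and 7.9, and the other two are not reassigned anywhere.

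The effect on the results is unknown. The documents do not allow the number of such tests, or the arm in which they fall, to be derived, so no direction of between-arm bias is claimed. The tabulated 'Yes' percentage is the same whether these subjects are labelled 'No' or 'Missing'. What changes is the count of confirmed negatives and, depending on how 'Missing' is handled, the set compared in the chi-square/Fisher test. The variable is a secondary safety assessment, and neither the primary analysis nor the sample size depends on it. The correction is worth making because it is specific and cheap, not because a large effect has been shown.

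**What to change.** In SAP 6.4, replace the closing clause with three outcomes: 'Yes' if any available difference exceeds its limit; 'No' only if all four differences are available and none exceeds its limit; 'Missing' in every other case. Requiring all four differences also covers an absent supine average.

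In SAP 7.9, state that the chi-square/Fisher test uses subjects classified 'Yes' or 'No', and report the number 'Missing' by arm and visit. The tabulated percentages can keep the 7.1 denominator.

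SAP v4.0 is identified in section 1.5 as post-unblinding, so the change should be dated as such and the result under the current 6.4 rule shown beside it.

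The cost is one derivation line, one sentence on the test and a second set of results. The test loses a few subjects. A partly missing test is kept when positive and set aside when not, so the rate among evaluable subjects can lean slightly upward; the counts of 'Missing' and the result under the current rule let a reader see by how much. A sensitivity analysis counting tests stopped for symptoms as 'Yes' is not proposed, because neither document says that a stopping reason is recorded.

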### **ECG**

The ECG diagnosis (normal, abnormal NCS, abnormal CS, not done, missing) will be used for the analysis.

### **Hematology, serum chemistry, and urinalysis**

See Appendix B of the protocol for a full list of hematology, serum chemistry, and urinalysis variables that will be used for analysis. Creatinine clearance will serve dual functions as a secondary efficacy endpoint (see Section 6.2) and a safety endpoint. For the latter, the Safety population will be used for the analysis.

## **6.5. Other Variables**

### **Pharmacokinetics**

The plasma concentration of amlodipine at Day 14, 24 ± hour post-dose will be used for analysis.

For the individual patient data listing of amlodipine plasma concentrations, all values below the LLOQ will be reported as BLQ, as in the bioanalytical report.

For the summary of non-transformed amlodipine plasma concentration values by treatment group by descriptive statistics (n, mean, SD, median, and range), as well as the t-test analysis of the non-transformed values and the box plot analysis of non-transformed values, all BLQ values will be treated as zero.

For the summary of log-transformed amlodipine plasma concentration values by treatment group by descriptive statistics (n, mean, SD, median, and range), as well as the t-test analysis of the log-transformed values, all BLQ values will be treated as 0.04 ng/mL rather than 0. Zero cannot be log-transformed. Assignment of the BLQ values to a nonzero number will allow computation of the log transformation. The selection of 0.04 ng/mL as the nonzero number for BLQ assignment was based on the LLOQ of the validated bioanalytical method (i.e., 0.05 ng/mL) and selecting the next lowest number at the hundredth decimal place.

## Baseline

Baseline measurements for the various parameters are defined as follows:

- a. ABPM baseline measurements are taken for 25 hours between Day -1 and Day 0, initiating at the Final Screening Visit and completing at Day 0 (prior to study drug administration).
- b. Baseline values for the following variables are taken on Day 0 prior to study drug administration:
  - Body weight\*
  - Orthostatic hypotension evaluation
  - Vital signs (clinic visit BP measurements, pulse rate, respiration rate, and oral body temperature)\*
  - Serum chemistry\*
  - Targeted physical examination
- c. Baseline values for the following variable are taken at the Initial Screening Visit (Day -14 to -10) will be the baseline for the following variables:
  - BMI
  - Hematology
  - ECG
  - Urinalysis
  - Comprehensive physical examination

\*Baseline measurement for body weight, vital signs, and serum chemistry is Day 0 (prior to study drug administration); however, if the baseline measurement is missing and there is a prior measurement recorded (i.e., Initial Screening Visit), this value will be carried forward and used as the baseline measurement.

## 7. Statistical Methodology

### 7.1. Handling of Missing Data

For ITT and mITT population, if at the time of the Day 7 clinic visit subjects have a too elevated BP to be able to continue safely in the study (i.e., SBP24h > 169 mmHg or DBP24h > 110 mmHg), blood will be drawn for renal profile testing, the study drug will be discontinued and the subjects will be instructed to resume taking their prescribed BP medication as directed by the study doctor or general practitioner. In case of missing data, LOCF techniques will be used as follows:

1. ITT population: LOCF from baseline (Day 0)
2. mITT population: LOCF from Day 6

Using this method, the end of study measurement is either Baseline, Day 6 or Day 13.

No specific analysis for withdrawn patients will be presented.

The number of patients with missing data will be presented under the “Missing” category, if present. Missing values will be included in the denominator count when computing percentages.

When continuous data are being summarized, only the non-missing values will be evaluated for computing summary statistics.

Missing or incomplete data will be treated as described in sections 5, 6.4, 6.5, 7.1, 7.9, 7.10. Other critical missing data will be discussed prior to treatment unblinding, if any. Decisions will be taken during the data review and will be fully documented in the Data Review Report.

The LOCF method of imputation will be applied for missing values in all ANCOVA models. This method will not be applied to the descriptive statistics.

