8.6 Hematology, Serum Chemistry, and Urinalysis

Blood and urine for clinical safety laboratory assessments will be collected at the initial screening visit, Day 0 (serum chemistry only), and on Day 14. The samples will be prepared using standard procedures. A detailed listing of the hematology, serum chemistry, and urinalysis tests that will be

performed is provided in Appendix B. A regional laboratory will perform the clinical laboratory tests.

In addition, at Day 7, blood will be collected for a subset of serum chemistry tests. Specifically, the testing will be limited to creatinine (and calculation of creatinine clearance) and electrolytes (sodium, bicarbonate, calcium, chloride, phosphorous, and potassium).

Also, if the subject's BP at Day 7 is too elevated for them to continue safely in the study (i.e., $SBP_{24h} > 169$ mmHg and/or $DBP_{24h} > 110$ mmHg), blood will be drawn for renal profile testing (non-fasting). The renal profile testing will include the following tests: creatinine, calcium, chloride, carbon dioxide, albumin, blood urea nitrogen (BUN), protein, phosphorus, glucose, and potassium.

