**j. Hematology, serum chemistry, and urinalysis**

For the majority of the hematology, serum chemistry, and urinalysis tests, the comparisons of the safety population data among treatment arms using Chi-square, binomial, and logistic analyses for dichotomous variables (e.g., negative/positive) and ANCOVA for continuous variables will not be done due to the limited number of subjects. The exceptions are serum creatinine and blood urea nitrogen (BUN), where comparisons between treatment arms will be performed using an ANCOVA model with change from baseline to Day 14 as the dependent variable, treatment as the fixed effect, and baseline as the covariate.

The laboratory reference range for assigning low "L" flags to the creatinine clearance results differed for the Celerion, Belfast laboratory (>90 mL/min) versus the centralized laboratory used for the remaining sites (ACM Global Central Laboratories;  $\geq 60$  mL/min). The serum chemistry shift table analysis will be based on the laboratory assigned flags (i.e., no reassignment of the Celerion, Belfast laboratory flags based on the ACM laboratory reference range will be made). The main body of the clinical study report will note the difference in the creatinine clearance reference range for the two

laboratories and will note by treatment group any cases where a Celerion, Belfast low creatinine clearance value would be reassigned as Normal if the  $\geq 60$  mL/min criterion was used.

Documentation of the differing creatinine clearance reference ranges for ACM and Celerion, Belfast is included in Appendix 16.1.10 of the clinical study report and in the individual subject laboratory reports that are included with the consolidated case report form PDF files, copies of which are included in the Trial Master File.

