### **Laboratory parameters**

Hematology, chemistry and urinalysis (including urine microscopy) parameters will be summarized for the Safety population by treatment group at each applicable visit (Initial Screening Visit, Day 0\*,

Day 7\*, and Day 14) by descriptive statistics as appropriate (i.e., n, mean, SD, median, and range for continuous data and frequency for categorical data). In addition, at each visit after baseline, change from baseline will be calculated and summarized for continuous data by descriptive statistics (n, mean, SD, median, and range). Baseline will be Day 0 if available, otherwise, the Initial Screening Visit assessment will be used.

\*The laboratory parameters on Day 0 and Day 7 were limited to serum chemistry tests (i.e., no hematology or urinalysis), and further, the serum chemistry tests at Day 7 were limited to creatinine (and calculation of creatinine clearance) and electrolytes (sodium, bicarbonate, calcium, chloride, phosphorous, and potassium).

Shift tables presenting the number and the percentage of patients in each bivariate category (Baseline versus Day 14) with regards to reference range (Low, Normal, High, missing) will be provided for all laboratory parameters by treatment group. Baseline will be Day 0 if available, otherwise, the Initial Screening Visit assessment will be used.

The laboratory reference range for assigning low “L” flags to the creatinine clearance results differed for the Celerion, Belfast laboratory ( $>90$  mL/min) versus the centralized laboratory used for the remaining sites (ACM Global Central Laboratories;  $\geq 60$  mL/min). The serum chemistry shift table analysis will be based on the laboratory assigned flags (i.e., no reassignment of the Celerion, Belfast laboratory flags based on the ACM laboratory reference range will be made). The main body of the clinical study report will note the difference in the creatinine clearance reference range for the two laboratories and will note by treatment group any cases where a Celerion, Belfast low creatinine clearance value would be reassigned as Normal if the  $\geq 60$  mL/min criterion was used.

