For serum creatinine and BUN, comparisons between treatment groups will be performed with an ANCOVA model with change from baseline to Day 14 as dependent variable, treatment as fixed effect and baseline as covariate. The number of patients and the number of patients considered in the model will be provided by treatment. P-values of the fixed effects and covariates will also be presented. The adjusted means for treatments and the relative 95% CIs will be presented. The difference between the adjusted means of the three treatment groups will be calculated with the relative 95% CI and p-value.

The primary comparison will be treatment group 1 compared to treatment group 2, and the key secondary comparison will be treatment group 1 compared to treatment group 3. In these analyses, the null hypothesis will be that there is no statistically significant difference in the change in the measured blood parameter (serum creatinine or BUN) from baseline to the end of treatment between the two treatment groups. Baseline will be Day 0 if available, otherwise, the Initial Screening Visit assessment will be used.

The listings and summary tables will use the clinical laboratory test names as they appear in the Study Data Tabulation Model dataset files (i.e., the Clinical Data Interchange Standards Consortium compliant clinical laboratory test names). Refer to “Note to File - Differences in Laboratory Test Names Between Testing Laboratory and Study Data Tabulation Model (SDTM) Files”, a copy of which is available in the Trial Master File.

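### Read literally, the SAP's LOCF rule scores most subjects without a Day 14 BUN as having exactly zero change, because BUN has no routine Day 7 value; carry-forward should be limited to post-dose values

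*SAP*

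**What the plan says.** SAP 7.1 sets one rule for covariance analyses: "The LOCF method of imputation will be applied for missing values in all ANCOVA models". It adds that the method is not used for descriptive statistics. It gives an origin for the carried value in two populations only: baseline for ITT and Day 6 for mITT.

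SAP 1.3.9 item j drops the between-arm comparisons for most laboratory tests. It then says: "The exceptions are serum creatinine and blood urea nitrogen (BUN), where comparisons between treatment arms will be performed using an ANCOVA model". SAP 7.9 (Laboratory parameters) defines the outcome: "For serum creatinine and BUN, comparisons between treatment groups will be performed with an ANCOVA model with change from baseline to Day 14". It also ranks the contrasts: "The primary comparison will be treatment group 1 compared to treatment group 2". Laboratory data are analysed in the Safety population.

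On timing, SAP 7.9 notes that "the serum chemistry tests at Day 7 were limited to creatinine (and calculation of creatinine clearance) and electrolytes", and Protocol 8.6 agrees. The full chemistry panel, which includes BUN (Protocol Appendix B), is drawn at Screening, Day 0 and Day 14 (Appendix A). The one planned Day 7 BUN is in the renal profile that Protocol 8.6 requires for subjects whose SBP24h exceeds 169 mmHg and/or whose DBP24h exceeds 110 mmHg. SAP 6.5 takes baseline chemistry from Day 0 before dosing, or from Screening if Day 0 is missing.

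**The concern.** Creatinine, body weight and clinic blood pressure all have a routine Day 7 value, so carrying forward gives a measurement made on study drug. BUN does not. Outside the group stopped for high pressure, the only values that can be carried to Day 14 were taken before the first dose.

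BUN and creatinine are the only two laboratory safety tests still compared between arms by a model. The celecoxib label in Protocol Appendix G (section 5.13) reports elevated BUN more often than on placebo, while noting that the clinical significance is not established. A rule that counts an unmeasured subject as unchanged pulls such a comparison toward no difference when loss is similar in the two arms. The text can also be programmed in two ways, which would give two different BUN tables.

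**Working it through.** **What the rule enters.** For a subject with no Day 14 BUN and no Day 7 renal profile:

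- Baseline is the Day 0 pre-dose value, or Screening if Day 0 is missing.
- The last observation is that same value.
- Imputed change = baseline − baseline = 0.

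**Expected effect on the contrast.** The documents give no BUN effect size, SD or missing rate, so there is no plan figure to reproduce. Let μ1 and μ2 be the true mean changes and m1 and m2 the shares filled. If values are missing at random:

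expected difference after filling = (1 − m1)μ1 − (1 − m2)μ2

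With m1 = m2 = m this is (1 − m)(μ1 − μ2). About 105 subjects at 3:3:1 gives 105 × 3/7 = 45 in each amlodipine arm.

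| Assumed m, each arm | Subjects filled (45 × m) | Share of true difference kept |
|---|---|---|
| 2% | 0.9 | 98% |
| 5% | 2.25 | 95% |
| 10% | 4.5 | 90% |

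**Simulation.** 4,000 trials per scenario, 45 per arm, change regressed on treatment and baseline, two-sided 0.05. Assumptions not in the documents: true difference 0.40 SD, no mean change in arm 2, baseline to Day 14 correlation 0.7, values missing at random.

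| Missing, arm 1 / arm 2 | Baseline fill: estimate, power | Observed only: estimate, power |
|---|---|---|
| 0 / 0 | 0.402, 74.5% | 0.399, 74.0% |
| 5% / 5% | 0.379, 71.8% | 0.401, 71.6% |
| 10% / 10% | 0.359, 68.3% | 0.403, 70.7% |
| 10% / 2% | 0.361, 67.2% | 0.400, 71.8% |
| 2% / 10% | 0.389, 73.7% | 0.398, 71.4% |

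The estimates follow the formula: 0.95 × 0.40 = 0.38; 0.90 × 0.40 = 0.36; 0.98 × 0.40 = 0.392. The simulation error on a power near 70% is √(0.7 × 0.3 / 4000) = 0.7 percentage points.

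A second set used 48 per arm, a true difference of 0.50 SD and correlation 0.6. At 10% / 10%, filling gave 0.451 (SE 0.158) and observed cases 0.502 (SE 0.173), with power 80.0% and 81.2%. Type I error stayed near 5%. At an assumed 15% / 5%, power was about 74% with filling and 80% without.

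Under equal loss the estimate and its standard error shrink together: 0.451 / 0.158 = 2.85 against 0.502 / 0.173 = 2.90. That is why power barely moves.

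**The case against.** The strongest reply is that no sentence says a pre-dose BUN becomes the Day 14 value. The baseline origin in SAP 7.1 is given for ITT, whereas laboratory data use the Safety population. The clinic blood pressure paragraph in SAP 7.9 carries Day 7 forward and uses Screening only to fill a missing baseline. The body weight and blood pressure paragraphs restate LOCF; the BUN paragraph does not. It also asks for the number of patients entering the model, which would fit dropping those without data. This stands as a caveat: filling with baseline is the literal reading, not the only possible one. It does not remove the point, since SAP 7.1 covers every ANCOVA and accepts baseline as an end-of-study value for ITT.

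The second reply is about size, and it largely stands. Treatment lasts 14 days, and Protocol 4.3 asks for Day 14 evaluations after withdrawal where feasible. Subjects stopped for high pressure also have a Day 7 BUN. Unimputed BUN summaries are reported by arm, and the shift tables have a missing category. The comparison is a safety analysis outside the gatekeeping sequence.

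A third reply is that observed-case analysis recovers the true difference in the simulations only because values were deleted at random. That is correct, and it limits what the fix can claim.

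**Conclusion.** The point holds as a modest defect in a stated rule. Taken literally, SAP 7.1 enters a zero BUN change for every subject with neither a Day 14 BUN nor a Day 7 renal profile. Under equal loss at random, the arm 1 v arm 2 difference shrinks by the share filled: 2%, 5% or 10% at assumed rates of 2%, 5% or 10%. Power changes by roughly one to two points at 10% loss, and type I error hardly moves. Unequal loss can cost more, about 4 to 6 points in the scenarios with heavier loss in arm 1, but nothing in the documents predicts such a pattern.

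Three stronger inferences are not supported:

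- **That the rule hides renal harm.** The attenuation is proportional to a share that may be very small, and the unimputed BUN data are reported alongside.
- **That the standard error is about 9% too small.** That figure compares 0.158 with 0.173, the standard errors of two different estimators. Against the filled estimator's own sampling SD of 0.162, the printed value is about 2% to 3% low (0.158 / 0.162 = 0.975).
- **That 10% of BUN values are expected to be missing.** The 10% in Protocol 10.9 is a recruitment margin, not a forecast of missing laboratory data.

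**What to change.** State in SAP 7.1 and 7.9 that LOCF in the safety ANCOVAs carries forward post-dose values only. Fit the BUN ANCOVA to subjects with a post-dose BUN: Day 14, or the Day 7 renal profile where taken. Report by arm how many subjects have none. SAP 1.5 describes version 4.0 as final and post-unblinding, so the change should be labelled as made after unblinding.

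The cost is a sentence or two in the SAP and one extra count in the table. The model loses the few subjects with no post-dose BUN. The result is unbiased only if missingness is unrelated to the unseen value; reporting the counts by arm lets a reader judge how far that matters.
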